4. STUDY DESIGN

We will perform an observational cohort study. The long-term neurodevelopmental outcome of children affected by FNAIT will be evaluated. All children born between 2002 and 2017 and diagnosed with FNAIT are eligible for follow-up assessment and will be invited for an assessment at our outpatient clinic. The FNAIT survivors will be collected in two cohorts; cohort 1 will consist of FNAIT survivors without antenatal treatment, cohort 2 will consist of FNAIT survivors that were antenatally anticipated and therefore IVIg treatment to the mother was given. A summary of our study design is presented in Figure 1.

Enrollment in our study will take place via the LUMC and Stichting Sanquin Bloedvoorziening. The LUMC is national referral center for intrauterine therapy and Sanquin is national reference laboratory to diagnose FNAIT. Retrospectively FNAIT cases will be collected and asked for permission directly or via referring specialist according to the procedures described in paragraph 12.2.

After informed consent, child cognitive functioning will be assessed with a formal psychological test of cognitive functioning described in table 2, chapter 9. According to age, the parents will complete a standardized behavioral and HRQoL questionnaire. Academic performance will be assessed by collecting the most recent CITO test scores from the Dutch Pupil monitoring system developed by the National Institute for Educational Measurement [14]. Assessment of the prevalence of possible late effects of IVIg on the immune system will be assessed by questionnaires about the prevalence of allergies, asthma, eczema and course of infections by questionnaires. Parents and children, when 12 years old or older, are asked for consent to request the medical letters from the maternity or neonatology ward to obtain perinatal and neonatal data.

Figure 1: Study design

5. STUDY POPULATION

5.1 Population (base)

All children born between 2002 and 2017 and diagnosed with FNAIT are eligible for this study. They will be invited for an assessment at our outpatient clinic. FNAIT cases that were not antenatally treated with IVIg will be eligible for the study (cohort 1), as well as FNAIT cases which were anticipated antenatally by maternal IVIg administration (cohort 2).

The retrospective study design might bias the results (e.g. survival and recall bias). However in our opinion this is the only feasible way to perform a long term development study in this disease. Between 2002 and 2017 the NOICH trial was performed, after this trial the dosage regime of IVIg treatment was reduced from 1.0 g/kg/week to 0.5 gr/kg/week. We do not think this will have important effects on the results of our study but will verify this effect by description of the maternal treatment dosage.

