1. SUMMARY

Rationale: Fetal and neonatal alloimmune thrombocytopenia (FNAIT) is a disease caused by allo-immunisation during pregnancy. If left untreated, FNAIT can lead to severe fetal intracranial haemorrhage. This complication can be prevented by weekly administration of intravenous immunoglobulin (IVIg) to the mother during pregnancy. Although treatment with IVIg is nowadays considered as the golden standard for the management of FNAIT, the exact mechanism of action of IVIg is still under debate. Most importantly, the long-term effects and safety of IVIg treatment in FNAIT have not yet been evaluated. The use of IVIg during pregnancy for FNAIT is therefore still 'off-label'. The medication leaflet of IVIg continues to state that there is insufficient knowledge on the use of this product during pregnancy, despite all the years of experience and implementation in virtually all international guidelines.

Knowledge on long-term development of FNAIT survivors with or without IVIg treatment is very limited but an important subject in the counselling of parents of newly diagnosed cases. A greater understanding of the long-term outcome and the effects of IVIg on child development is necessary.

Objective: To evaluate the long-term neurodevelopmental outcome in two groups of children with FNAIT. First, children with unanticipated disease 'index cases' that were born without maternal IVIg administration during pregnancy. Second, children with anticipated disease; their mothers were treated with IVIg during pregnancy.

Study design: Observational cohort study.

Study population: The study population consists of two different cohorts of FNAIT children born in the Netherlands between 2002 and 2017.

- Cohort 1: The first cohort of children will consist children with unanticipated disease, 'index cases that were born without maternal IVIg administration during pregnancy.'
- Cohort 2: Second cohort will consist of children with anticipated disease; their mothers were treated with IVIg during pregnancy.

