3. OBJECTIVES

3.1 Primary objective(s)

The primary objective is to determine the cognitive test score of children diagnosed with FNAIT without and with antenatal treatment. We will assess the neurodevelopmental outcome, with IQ score as outcome measure, of two groups:

Cohort 1: To evaluate the natural history of FNAIT, we will include in this first cohort all FNAIT survivors without antenatal treatment. Our hypothesis is that the cognitive test score in this cohort will be lower compared to the general population.

Cohort 2: To evaluate the safety and benefit of IVIg treatment, the IQ score in all FNAIT survivors treated with antenatal IVIg treatment will be determined. Our hypothesis is that the cognitive test score in this cohort is similar to the general population.

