5.3 Exclusion criteria

A potential subject who meets any of the following criteria will be excluded from participation in this study:

- Children born with congenital and/or chromosomal abnormalities.
- Children that passed away before inclusion.

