5.4 Sample size calculation

Of note, performing sample size calculations in the context of this rare disease is difficult since literature is scarce and heterogeneous.

We performed two different sample size calculations for the two cohorts.

Cohort 1: Using the literature to date we estimated that the IQ score of FNAIT survivors without antenatal treatment is lower, that is 92 versus average (100) in the normal population. To show a difference in IQ score between FNAIT survivors without IVIg treatment compared to a fixed average of 100, we performed a sample size calculation for a one-sample t-test. We calculated that a minimum group size of 39 was needed to show a mean difference of 7 IQ points with a power of 0.8 and a significance of 0.05. We assume a standard deviation (SD) of 15 for the IQ score.

Cohort 2: In the FNAIT survivors with antenatal treatment we expect no difference in IQ score between cases and the national average. To show that there is no difference IQ score in anticipated IVIg treatment compared to the Dutch average we perform a non-inferiority calculation by a one-sample t-test. In this case we need a sample size of 39 children with a non-inferiority margin of 7 IQ points, with a power of 0.8 and a significance level of 0.025. We assume a standard deviation (SD) of 15 for the IQ score.

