11. STATISTICAL ANALYSIS

Continuous parametric data will be presented with mean \pm standard deviation (SD) or median with interquartile range (IQR) as appropriate. Categorical data will be presented as counts and percentages within each study group.

The cognitive test score of both cohorts will be compared with the Dutch average by using a linear regression model. The following potential confounders for cognitive development (IQ score) identified in earlier research will be used in the analysis;

- Sex
- Gestational age at birth
- Small for gestational age
- Neonatal morbidity
- Level of education of the parents

In second cohort; the FNAIT survivors with IVIg treatment atopic constitution and the course of infections will be assessed in a secondary analysis.

In the assessment of course of infections the following confounders will be used in the analysis by using a linear regression model;

- Day-care visit
- Smoking in a household
- Time of the year that the questionnaire was filled in

In the analysis of allergies and asthma the following confounders will be used in the analysis by using a linear regression model;

- Presence of a first degree family member with asthma eczema or allergy
- Smoking in a household

All data is analysed with IBM SPSS Statistics version 24 (IBM Software, NY, USA, 2016).

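### Neither cohort is limited to one child per mother, yet sizing and analysis treat children as independent; if siblings enrol in the same cohort, the standard error is slightly too small

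*Combined protocol and SAP*

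**What the plan says.** Eligibility is defined at the level of the child. Section 5.1 states: "All children born between 2002 and 2017 and diagnosed with FNAIT are eligible for this study". Section 3.1 puts all survivors without antenatal treatment into cohort 1, and for cohort 2 says: "To evaluate the safety and benefit of IVIg treatment, the IQ score in all FNAIT survivors treated with antenatal IVIg treatment will be determined". Section 4 adds that "cohort 2 will consist of FNAIT survivors that were antenatally anticipated and therefore IVIg treatment to the mother was given".

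The inclusion criteria in 5.2 concern diagnosis, age, residence, parental authority and consent. Section 5.3 has two exclusions: "Children born with congenital and/or chromosomal abnormalities", and death before inclusion. None of these refers to siblings, twins or the number of children per mother.

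Section 5.4 sizes both cohorts with a one-sample t-test. For cohort 2 it says: "In this case we need a sample size of 39 children with a non-inferiority margin of 7 IQ points", with power 0.8, significance level 0.025 and SD 15. It makes no allowance for clustering. Section 11 says: "The cognitive test score of both cohorts will be compared with the Dutch average by using a linear regression model". The model has five covariates, one of which belongs to the family ("Level of education of the parents"). There is no family term, no robust variance and no rule for choosing among siblings. The plan does not say that sibling sets will be counted or reported.

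**The concern.** A one-sample t-test and an ordinary regression are valid when each child contributes independent information. Two children of one mother share genes and home, so their IQ scores are likely to be positively correlated. Two treated children of one mother, from two treated pregnancies or a treated twin pregnancy, both qualify for cohort 2. Two untreated siblings or twins both qualify for cohort 1. It is plausible that treated siblings occur: a mother whose pregnancy was anticipated was already known to be at risk, and the window covers 16 birth years. This is an inference, because the documents give no count.

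If such pairs enrol, the reported standard error is too small. In cohort 2 the lower confidence limit is then too high and non-inferiority is declared slightly too easily, which favours the conclusion on safety and benefit of IVIg. In cohort 1 a deficit against 100 is declared slightly too easily.

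**Working it through.** **Inputs from the documents (5.4, cohort 2):** n = 39, margin 7, SD 15, power 0.8, level 0.025, true difference 0. **Assumed, not in the documents:** k sibling pairs among the 39 children (0 to 6) and ICC 0.3 to 0.4.

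**Step 1: the plan's own figure.** The exact one-sample t-test (noncentral t) at one-sided 0.025 has power 0.811 at n = 39 and 0.7999 at n = 38, so 39 reproduces as the minimum. At one-sided 0.05 the answer would be 30, so 0.025 is a one-sided level.

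**Step 2: variance with k pairs.** Of the 39 children, 2k are in pairs, so the variance of the mean is multiplied by

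DEFF = 1 + ICC × 2k/39.

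- 1 pair, ICC 0.3: 1 + 0.3 × 2/39 = 1.015
- 4 pairs, ICC 0.3: 1 + 0.3 × 8/39 = 1.062
- 6 pairs, ICC 0.4: 1 + 0.4 × 12/39 = 1.123

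The true standard error exceeds the reported one by the factor √DEFF.

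**Step 3: lower limit.** The reported standard error is about 15/√39 = 2.402 and the t quantile on 38 degrees of freedom is 2.024. The lower limit is too high by 2.024 × 2.402 × (√DEFF − 1) = 4.862 × (√DEFF − 1).

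**Step 4: actual level.** Approximately 1 − Φ(1.96/√DEFF), checked by simulating the ordinary t-test at n = 39 with true mean 93 (1.5 million runs per scenario).

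| Pairs, ICC | DEFF | True SE larger by | Lower limit too high by (IQ points) | Level, formula | Level, simulated |
|---|---|---|---|---|---|
| none | 1 | 0% | 0 | 0.025 | 0.025 |
| 1, 0.3 | 1.015 | 0.8% | 0.04 | 0.0259 | 0.0258 |
| 4, 0.3 | 1.062 | 3.0% | 0.15 | 0.0286 | 0.0285 |
| 6, 0.4 | 1.123 | 6.0% | 0.29 | 0.0322 | 0.0322 |

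**Step 5: power, kept apart from the level.** Simulated with the siblings present, the test as planned has power of about 0.81, 0.80 and 0.80 in the three sibling scenarios, against 0.81 with none. A valid correction works with the effective sample size 39/DEFF = 38.4, 36.7 and 34.7, where power is 0.804, 0.786 and 0.761.

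**Step 6: does the correction work?** Mother-clustered standard errors (CR2 with Satterthwaite degrees of freedom, 400,000 runs) bring the level back to 0.025 to 0.026 in these scenarios, with power 0.80, 0.78 and 0.76. Keeping one child per mother gives a level of 0.025 and power 0.80, 0.77 and 0.74.

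**The case against.** The strongest objection is that the problem is hypothetical and small. No section says that treated siblings or twins exist in either cohort. Both the pair counts and the ICC are assumed, and the largest shift shown is 0.29 points, about 4% of the margin. With one pair, the uncorrected level of 0.026 barely differs from what the clustered method achieves. All of this stands, and it sets the priority.

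Two mitigating arguments stand in part. Parental education in the section 11 model may absorb some of the family correlation, but the one-sample test that 5.4 sizes has no covariates. Siblings of different ages may be tested on different instruments (9.1.1), which may also lower the correlation.

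Section 11 states no margin, no level and no non-inferiority test, so the link from 5.4 to the analysis is inferred.

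A reader might infer four stronger things that the documents do not support:

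- *That the 0.025 level is breached.* It is exceeded only if siblings enrol in the same cohort with positively correlated scores. Ten pairs with ICC 0.4 would give 0.037, but nothing in the documents points to so many.
- *That the planned test loses power.* It does not, beyond about 0.01. The fall to 0.76 is the cost of correcting.
- *That 39 is miscalculated.* It reproduces under independence.
- *That an untreated index child and a later treated sibling cause the error.* Section 1 describes cohort 1 thus: "First, children with unanticipated disease 'index cases' that were born without maternal IVIg administration during pregnancy". Such a link runs across cohorts and does no harm, because each cohort is compared separately with a fixed value.

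**Conclusion.** The point holds as a conditional and minor one. The omission is certain and applies to both cohorts: there is no one-child-per-mother rule, no twin exclusion, no method that allows for siblings and no commitment to count them. With positive sibling correlation, the resulting error goes in one direction, towards too small a standard error. Its size in cohort 2 depends wholly on the assumed 1 to 6 pairs among 39 children and ICC of 0.3 to 0.4, and on the inferred use of the 5.4 non-inferiority comparison. The remedy is cheap, and without a count of sibling sets no reader of the results could judge whether the issue arose. Priority: low.

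**What to change.** 1. Identify children who share a mother through the coding key held by the investigator (13.1), supported by the obstetric records. Report the number of mothers and of sibling sets in each cohort.
2. In any cohort that contains siblings, use standard errors clustered on mother with a small-sample correction (for example CR2 with Satterthwaite degrees of freedom) for the comparison with 100.
3. Add a sensitivity analysis with one randomly chosen child per mother.
4. State in 5.4 that 39 assumes independent children.

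**Cost.** No new assessment of any child is needed. Maternal age, obstetric history and parity (Table 1) help to confirm a link but do not identify a mother, and the obstetric letter depends on her consent (9.3), so the key should carry the linkage. Where siblings are present, intervals are slightly wider on average, though not always: with ICC 0.3 the clustered standard error is smaller than the ordinary one in about 40% of datasets with 1 pair and 29% with 4 pairs. Power falls to about 0.76 to 0.80 in the scenarios above. Software other than SPSS 24 may be needed for the correction. If no siblings enrol, the analysis is unchanged.

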5.2 Inclusion criteria

In order to be eligible to participate in this study, a subject must meet all of the following criteria:

- Children diagnosed with FNAIT during pregnancy or postnatal, at moment of inclusion 2 to 16 years of age.
- Children living in the Netherlands.
- Parents or guardian aged ≥ 18 years old, with parental authority.
- Written informed consent form both parents with, form being approved by Ethic Committee.

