No long-term standardized follow-up studies were performed on FNAIT cases without antenatal treatment and/or ICH. The natural course of the disease and long-term effects of thrombocytopenia on the developing fetus and newborn are unknown. FNAIT is defined as a disease caused by alloantibodies, resulting in thrombocytopenia and a risk of bleeding in the neonate. In the last years, evidence is increasing that the maternal alloantibodies can also bind to the fetal endothelium and may impair angiogenesis in the developing fetuses [8] [9]. It

is not known at which moment in pregnancy the developing brain is most vulnerable for damage induced by these kind of alloantibodies. The timing in fetal life FNAIT associated ICH ranges from 23 to 42 weeks [10], but small bleeding may not be diagnosed. It may also be that these type of alloantibodies not lead to ICH but to other type of cerebral damage. These lesions can remain subclinical directly after birth but lead to developmental delay on the long term. This knowledge can be of great interest when counseling parents with a risk of FNAIT or in writing guidelines.

For 3 decades a nationwide screening on FNAIT to detect pregnancies with alloantibodies in time and start treatment to prevent bleedings is being discussed. If alloantibodies lead to cerebral damage on the long term also in patients without large ICH this might have large implications in the debate on the introduction of a national screening programme. Therefore we want to underline that more knowledge about the long-term development of FNAIT survivors is required.

The Leiden University Medical Center (LUMC), a national fetal therapy center in The Netherlands, has a close and long-lasting collaboration with Sanquin. This collaboration offers a unique opportunity to evaluate a large and complete cohort of children with FNAIT. LUMC and Sanquin are both nationwide referral centers for FNAIT and committed to improve timely detection of high-risk cases who need intra-uterine therapy. In our opinion we have a duty as a national expertise center to assess long-term outcome in children with FNAIT and describe the natural history of children affected by FNAIT and the long term effects of a given therapy.

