12.2 Recruitment and consent

The investigator will identify potential subjects according to the aforementioned criteria.

Eligible patients are informed about the study and are asked for their participation.

Enrolment will take place in two ways;

- First directly via the LUMC, the LUMC is national referral center for intrauterine therapy. Parents of children that survived FNAIT will be invited to participate by sending a patient information letter and information leaflet for children. In this way, the parents will be informed that they will be contacted by phone approximately two weeks after sending the information letter.
- Secondly patients will be asked via Stichting Sanquin Bloedvoorziening, Sanquin is the national reference laboratory to diagnose FNAIT. Retrospectively all FNAIT cases are collected in the Laboratory of platelet and leukocyte serology of Sanquin. Referring specialists (mostly pediatricians) will be asked to obtain permission from the parents to inform them about our study by letter enclosed by the patient information leaflet. If parents do not object to be informed they will be contacted by our research team approximately two weeks after sending this letter.

When parents wish not to be approached by our research team they can indicate this by responding by e-mail, phone or reply letter. Informed consent is obtained from all patients who are willing to participate. In case of minors both parents or their guardian will be asked for participation and informed consent. The patient information letter and informed consent form will be attached as a separate document. If informed consent is given, assessment will be planned. At most, 3 attempts will be made to contact parents by phone. It is expected that enrollment for this study will cover a period of one year.

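### Cohort 1 could take in children tested for FNAIT because of a later developmental problem, and the plan neither records nor examines this

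*Combined protocol and SAP*

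**What the plan says.** The inclusion criterion in section 5.2 is "Children diagnosed with FNAIT during pregnancy or postnatal, at moment of inclusion 2 to 16 years of age". Section 5.1 is equally broad: "All children born between 2002 and 2017 and diagnosed with FNAIT are eligible for this study". The only exclusions in section 5.3 are "Children born with congenital and/or chromosomal abnormalities" and "Children that passed away before inclusion".

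Section 3.1 defines cohort 1 and its purpose: "To evaluate the natural history of FNAIT, we will include in this first cohort all FNAIT survivors without antenatal treatment". The stated hypothesis is a cognitive score below that of the general population.

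On the case source, section 12.2 says: "Retrospectively all FNAIT cases are collected in the Laboratory of platelet and leukocyte serology of Sanquin".

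Table 1 (section 3.3) lists obstetric, neonatal, laboratory, outcome and demographic items, but not the date of the FNAIT work-up or the reason for it. Table 3 defines many terms but not an FNAIT diagnosis. Section 11 adjusts IQ for sex, gestational age, small for gestational age, neonatal morbidity and parental education. None of these describes how or when the child was identified.

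**The concern.** Cohort 1 is meant to show the natural history of untreated FNAIT. That requires entry not to depend on the outcome. A child diagnosed at birth for a low platelet count or bleeding meets this condition. A child whose work-up was requested much later, because of delay or an old brain lesion, does not: the poor outcome led to the diagnosis, and the diagnosis led to entry.

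The protocol's own rationale makes such a request conceivable. Section 2 says of possible antibody-related brain damage: "These lesions can remain subclinical directly after birth but lead to developmental delay on the long term".

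Children admitted this way would pull mean IQ down, toward the cohort 1 hypothesis, and push NDI incidence up. Cohort 2 was identified before birth, so this route does not apply to it. A difference seen between the cohorts could then partly reflect how children were found. Section 2 links the results to parental counselling and the national screening debate, so the cause of a low mean matters.

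**Working it through.** **1. Does any text close the gap?**
- Eligibility (5.1, 5.2): no age limit at diagnosis, no required neonatal presentation, no restriction on the reason for testing.
- Exclusions (5.3): nothing on late or symptom-prompted diagnosis.
- Definitions (Table 3): FNAIT diagnosis not defined.
- Data (Table 1): date and reason not listed.
- Analysis (11): no adjustment or sensitivity analysis for either.
- Acknowledged biases (5.1): survival and recall bias are given as examples. Selection by reason for testing is not mentioned.

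The gap is not closed anywhere.

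**2. The plan's own figure.** Inputs from section 5.4: difference 7, SD 15, power 0.8, significance 0.05, one-sample t-test against 100. With a two-sided test and the noncentral t distribution, the smallest n is 39 (power 0.811). This matches the stated 39, so that test is used below.

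**3. What counts as a significantly low mean.** Standard error = 15/√39 = 2.40. Multiplying by the two-sided 5% critical t value on 38 degrees of freedom gives 4.86. At SD 15, an observed mean about 4.9 points below 100 is significant.

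**4. Effect of k outcome-prompted children.** The documents give neither their number k nor their deficit d, so both are assumptions. All other children are taken to have mean 100 and SD 15.

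Mean shift = k × d / 39. The chance of a significantly low result comes from simulation (100,000 runs, n = 39). Repeat runs agreed to within about 0.2 percentage points.

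| k | d | Mean shift | Chance of a significantly low result |
|---|---|---|---|
| 0 | – | 0 | about 2.5% |
| 1 | 40 | 40/39 = 1.0 | about 4% |
| 2 | 30 | 60/39 = 1.5 | about 6% |
| 2 | 40 | 80/39 = 2.1 | about 7% |
| 4 | 30 | 120/39 = 3.1 | about 15% |
| 4 | 40 | 160/39 = 4.1 | about 20% |

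With a milder deficit of 15 points, k = 4 gives a shift of 60/39 = 1.5 points and about 8%.

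**5. What it would take to produce the whole planned effect.** A 7-point deficit from this route alone needs k = 7 × 39 / d. That is 6.8 children at d = 40 and 9.1 at d = 30, roughly 17% to 23% of 39.

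**6. NDI.** Each such child who meets the NDI definition adds 1/39 = 2.6 percentage points to the incidence. Four would add 4/39 = 10.3.

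**The case against.** **No such child is shown to exist.** This stands. A reader might infer from the open criterion that cohort 1 does contain outcome-prompted cases. The documents support only that it could. Section 2 describes FNAIT as thrombocytopenia with a bleeding risk in the neonate, and its sentence on silent lesions is a hypothesis about disease course, not about why children are tested. That background makes late diagnoses less likely, but it is not an eligibility rule.

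**The number 39 is a minimum.** This stands in part. In a larger cohort the same few children would move the mean less, but the same proportion would move it equally.

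**Much can be recovered from planned data.** Table 1 includes the platelet count directly after birth, bleeding signs, ICH and convulsions. Section 9.3 brings in laboratory data from the time of diagnosis and the medical letters. These would help identify children without neonatal presentation, but they do not state why testing was requested, and no analysis uses them for this purpose.

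**A low score in such a child may be a true effect of FNAIT.** This stands. The child then belongs to the target population but is over-represented, and calling the result falsely low is right only under the assumption that the other children average 100. The net bias is also not fixed: excluding children who died may raise the mean.

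**The primary analysis should be limited to neonatal work-ups.** A reader might infer this remedy, but it does not fit the plan. Section 3.1 states that "we will include in this first cohort all FNAIT survivors without antenatal treatment". Removing every child with a neurological finding would also remove neonates worked up for ICH or convulsions, who are part of the disease course, and would bias mean IQ upward.

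**Conclusion.** The gap is real, and its effect on the cohort 1 mean is toward the hypothesis. Section 5.2 leaves timing and reason of diagnosis open, and neither Table 1 nor section 11 deals with them.

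The size is unknown. It may be nil. The upper end of the range, about 4 points and a 20% chance of a falsely low result, requires about one child in ten (4 of 39) to have entered this way with a 40-point deficit, and the rest to average 100. It also assumes a two-sided 5% one-sample t-test, whereas section 11 plans a linear regression.

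The documents do not support saying that the cohort 1 result will be biased, or that the primary population is wrong. They do support saying that, as planned, a low mean IQ could not be separated from selection by reason for testing. This is a low-cost improvement to how the result can be read.

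**What to change.** 1. Add two items to Table 1: the date of the FNAIT diagnostic work-up and the reason it was requested. Take them from the laboratory data at diagnosis and the requested medical letters, where available. The documents do not say that the reference laboratory holds request reasons for past cases, so completeness should be reported.
2. Keep all untreated survivors as the cohort 1 primary population.
3. Prespecify in section 11 a cohort 1 sensitivity analysis of mean IQ and NDI that excludes only children whose work-up was requested after the neonatal period because of a neurological or developmental problem. Define the neonatal period in days. Retain children worked up within it, including for ICH or convulsions, and children diagnosed later for other reasons.
4. Report the excluded children separately, and state in advance how children with an unknown date or reason are handled.

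Cost: two data fields, which may be incomplete for older cases, and one extra analysis. Recruitment and the sample size do not change. If no such child is found, the fields show it and the primary result is easier to defend.
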